9.6.3 Complete Response Rate

Complete Response Rate (CRR) will be defined as the proportion of patients with a best overall response of CR. The percentage of CRR with its 95% CI will be presented.

9.6.4 Relapse-free Survival

RFS will be defined among CR patients as the time from the earliest date of first complete response until the first date of either disease relapse or death due to any cause. The date of disease progression will be defined as the earliest date of disease progression based on central review. For patients who have not progressed or died at the time of the analysis, censoring will be performed using the date of the last valid disease assessment. The data will be analyzed by the Kaplan-Meier method. The median duration of response and 95% CI will be presented. Further details will be outlined in the SAP.

9.6.5 Progression-Free Survival

PFS will be defined among all treated patients as the time from first dose of study drug until the first date of either disease progression or death due to any cause. The date of disease progression will be defined as the earliest date of disease progression based on central review. For patients whose disease has not progressed at the time of the analysis, censoring will be performed using the date of the last valid disease assessment. The data will be analyzed by the Kaplan-Meier method. The median PFS time and 95% CI will be presented. Further details will be outlined in the SAP.

9.6.6 Overall Survival

Median OS will be defined as the time from the beginning of study drug treatment until death due to any cause. For patients who have not died at the time of the analysis, censoring will be performed using the date the patient was last known to be alive. The data will be analyzed by the Kaplan-Meier method. The median OS and 95% CI will be presented. Further details will be outlined in the SAP.

9.6.7 Subgroup analysis

Subgroup analyses will be performed for ORR, DOR, CR, RFS, PFS, and OS using the following variables if appropriate

- Demographic variables: age group, gender, race, and country
- Baseline disease characteristics: tumor staging, and subtype
- Number of prior systemic therapies and response to prior systemic therapies

Other subgroup analysis factors may be evaluated as appropriate and the details will be provided in SAP.

9.7 Safety Analyses

Safety analyses will be presented descriptively.

9.7.1 Adverse Events

The focus of AE summarization will be on TEAEs. A TEAE is defined as an AE that occurs or worsens in the period extending from the first dose of study drug to 30 days after the last dose of study drug or start of new anti-cancer therapy, whichever is earlier.

TEAEs will be summarized. Summary tables will be presented to show the number of patients reporting TEAEs by severity grade and corresponding percentages. A patient who reports multiple TEAEs within the same Preferred Term (or System Organ Class) is counted only once for that Preferred Term (or System Organ Class) using the worst severity grade.

Separate summaries will be prepared for TEAEs classified as severe or life-threatening (Grade 3 or higher); study drug-related AEs; AEs leading to treatment interruption, modification, or discontinuation; serious AEs; and death. Dose interruptions, reductions, and relative dose intensity will also be summarized.

9.7.2 Clinical Laboratory Results

Clinical hematology, coagulation panel, biochemistry, and urinalysis data will be summarized at each scheduled assessment. Shifts for clinical laboratory results that can be graded according to CTCAE v4.0 (or more recent) will be summarized by CTCAE grade. Shifts for other numeric laboratory results will be by high/normal/low flag. Shifts for all other laboratory results will be by normal/abnormal flag.

Summaries by visit will include data from scheduled assessments, and all data will be reported according to the nominal visit date for which it was recorded. Unscheduled data will be included in “worst-case post-Baseline” summaries, which will capture a worst case across all scheduled and unscheduled visits after the first dose of study drug. Further details will be provided in the SAP.

9.7.3 Additional Safety Assessments

The results of scheduled assessments of vital signs, physical examinations, ECOG performance status, and 12-lead ECGs will be summarized. All data will be reported according to the nominal visit date for which it was recorded (i.e., no visit windows will be applied). Unscheduled data will be included in “worst case” summaries, which will capture a worst case across all scheduled and unscheduled visits after the first dose of study drug. All data will be listed. Further details will be provided in the SAP.

9.8 Pharmacokinetic Analyses

The PK profile may include, but is not limited to, determination of: maximum concentration (C_{max}), area under the concentration-time curve from time zero to the end of the dosing interval ($AUC_{0-\tau}$), area under the concentration-time curve from time zero to infinity ($AUC_{0-\infty}$), clearance (CL), and accumulation index (AI).

[figure not shown]
PK parameters will be determined for all PK-evaluable patients using a non-compartmental method with Phoenix WinNonlin (Certara USA, Inc., Princeton, NJ, US) or other appropriate software. Supplemental population PK analyses will be undertaken and reported separately to characterize the PK parameters for the typical patient and to identify covariate factors which influence drug disposition.

Demographic data for the PK population will be summarized. Potential correlations of PK parameters to baseline characteristics and safety observations will be assessed but may be reported separately. In addition, the influence of loncastuximab tesirine PBD-conjugated antibody and unconjugated warhead SG3199 concentrations on the QTc interval will be assessed but reported separately.

9.9 Immunogenicity Analyses

A tiered immunogenicity strategy (Figure 2) will be undertaken to evaluate ADAs by screening and confirmatory assays with titer evaluation, followed by characterization and evaluation of neutralizing capacity as needed. ADA sample collection, banking, and testing in validated and to be validated assays will be according to the new FDA Draft Guidance for Industry (April 2016): ‘Assay Development and Validation for Immunogenicity testing of Therapeutic Protein Products’.

Figure 2. Anti-drug Antibody Tiered Immunogenicity Testing Strategy

Abbreviations: ADA, anti-drug antibody; ADC, antibody-drug conjugate; BSA, bovine serum albumin; mAb, monoclonal antibody; PK, pharmacokinetics.

Results from ADA testing will include tabular summarization for number/proportion of patients with positive pre-dose ADA response, number of patients with post-dose ADA response only, and number of patients with positive ADA response at any time. The denominator will be the total number of patients tested for ADAs in the study.

10 Data Management and Quality Assurance

The Investigator will maintain accurate source documentation including patient medical records, laboratory reports, ECG strips, and patient diaries.

Investigative site qualified personnel will enter patient data into an EDC system. The analysis data sets will be a combination of these data and data from other sources.

Clinical data management will be performed in accordance with applicable standards and data cleaning procedures to ensure the integrity of the data (e.g., removing errors and inconsistencies in the data). AEs will be coded using the Medical Dictionary for Regulatory Activities (MedDRA). Concomitant medications will be coded using the world health organization (WHO) Drug Dictionary.

After database lock, each study site will receive information about all of their site-specific eCRF data as entered into the EDC system for the study, including full discrepancy and audit history. Additionally, a copy of study data from all sites will be created and sent to the Sponsor for storage. The CRO will maintain a duplicate copy for its records. In all cases, patient initials will not be collected or transmitted to the Sponsor.

For detailed instruction on data entry procedures and timelines, please refer to the eCRF Completion Guidelines.

11 Ethical, Regulatory, and Study Management Considerations

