Further evaluate the efficacy of loncastuximab tesirine	
 • DOR defined as the time from the first documentation of tumor response to disease progression or death • CR rate defined as the percentage of treated patients with a BOR of CR • Relapse-free survival (RFS) defined as the time from the documentation of CR to disease progression or death • PFS defined as the time between start of treatment and the first documentation of recurrence, progression, or death • OS defined as the time between the start of treatment and death from any cause
Characterize the safety profile of loncastuximab tesirine	
 • Frequency and severity of adverse events (AEs), and SAEs • Changes from baseline of safety laboratory variables, vital signs, ECOG performance status, and 12-lead electrocardiograms (ECGs)
Characterize the pharmacokinetic (PK) profile of loncastuximab tesirine	Concentrations and PK parameters of loncastuximab tesirine total antibody, PBD-conjugated antibody, and unconjugated warhead SG3199
Evaluate the immunogenicity of loncastuximab tesirine	Anti-drug antibody (ADA) titers and, if applicable, neutralizing activity to loncastuximab tesirine after treatment with loncastuximab tesirine
Evaluate the impact of loncastuximab tesirine treatment on health-related quality of life (HRQoL)	Change from baseline in HRQoL as measured by EuroQoL-5 Dimensions-5 Levels (EQ-5D-5L) and Functional Assessment of Cancer Therapy - Lymphoma (FACT-Lym)
[REDACTED]	[REDACTED]
[REDACTED]	[REDACTED]

4 Study Design

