5.2 Exclusion Criteria

1. Previous treatment with loncastuximab tesirine
2. Known history of hypersensitivity to or positive serum human ADA to a CD19 antibody
3. Pathologic diagnosis of Burkitt lymphoma
4. Bulky disease, defined as any tumor ≥ 10 cm in longest dimension
5. Active second primary malignancy other than non-melanoma skin cancers, non-metastatic prostate cancer, in situ cervical cancer, ductal or lobular carcinoma in situ of the breast, or other malignancy that the Sponsor's medical monitor and Investigator agree and document should not be exclusionary
6. ASCT within 30 days prior to start of study drug (C1D1)
7. AlloSCT within 60 days prior to start of study drug (C1D1)
8. Active graft-versus-host disease
9. Post-transplant lymphoproliferative disorders
10. Active autoimmune disease, including motor neuropathy considered of autoimmune origin and other central nervous system (CNS) autoimmune disease
11. Known seropositive and requiring anti-viral therapy for human immunodeficiency (HIV) virus, hepatitis B virus (HBV), or hepatitis C virus (HCV).
Note: Testing is not mandatory to be eligible
12. History of Stevens-Johnson syndrome or toxic epidermal necrolysis

13. Lymphoma with active CNS involvement at the time of screening, including leptomeningeal disease
14. Clinically significant third space fluid accumulation (i.e., ascites requiring drainage or pleural effusion that is either requiring drainage or associated with shortness of breath)
15. Breastfeeding or pregnant
16. Significant medical comorbidities, including but not limited to uncontrolled hypertension (blood pressure [BP] $\geq 160/100$ mmHg repeatedly), unstable angina, congestive heart failure (greater than New York Heart Association class II), electrocardiographic evidence of acute ischemia, coronary angioplasty or myocardial infarction within 6 months prior to screening, uncontrolled atrial or ventricular cardiac arrhythmia, poorly controlled diabetes, or severe chronic pulmonary disease
17. Major surgery, radiotherapy, chemotherapy or other anti-neoplastic therapy within 14 days prior to start of study drug (C1D1), except shorter if approved by the Sponsor
18. Use of any other experimental medication within 14 days prior to start of study drug (C1D1)
19. Planned live vaccine administration after starting study drug (C1D1)

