8.4.1 Pharmacokinetics

The concentration in serum of loncastuximab tesirine (total antibody), PBD-conjugated antibody, and unconjugated warhead SG3199 will be assessed by a central laboratory designated by the Sponsor using validated bioanalytical methods.

Approximately 6 mL of whole blood will be collected as per Table 1 and Table 5. Blood should be drawn from a vein away from the one used for study drug infusion.

PK samples must be stored at -70°C. Please refer to the laboratory manual for detailed instructions regarding specimen handling and shipment.

At timepoints coinciding with ECG collection, PK blood collection should occur immediately after the end of the ECG recording and, when applicable, after vital signs. If a patient experiences Torsade de Pointes, additional PK samples (e.g., unscheduled) should be collected.

Table 5. Sampling Schedule for PK and ADA

Cycle	Day	PK timepoint (window)	ADA timepoint (window)
C1	D1	Pre-dose (preferably within 2 h prior to start of infusion) EOI (-5 to +10 min) Post-dose* 4 h (± 10 min)	Pre-dose (preferably within 2 h prior to start of infusion)
	D8	Post-dose* 168 h (± 48 h)	-
	D15	Post-dose* 336 h (± 48 h)	Post-dose* 336 h (± 48 h)
C2	D1	Pre-dose (within 2h prior to start of infusion) EOI (-5 to +10 min) Post-dose* 4 h (± 10 min)	Pre-dose (within 2 h prior to start of infusion)
	D8	Post-dose* 168 h (± 48 h)	-
	D15	Post-dose* 336 h (± 48 h)	-
C3	D1	Pre-dose (within 2 h prior to start of infusion) EOI (-5 to +10 min)	Pre-dose (within 2 h prior to start of infusion)
C5, C7, ... every other cycle	D1	Pre-dose (within 2 h prior to start of infusion)	Pre-dose (within 2 h prior to start of infusion)
EOT		At any time during visit day	At any time during visit day
Unscheduled		Any time	Any time (if applicable, close to PK sample)

Abbreviations: ADA, anti-drug antibody; EOI, end of infusion; EOT, end of treatment; PK, pharmacokinetics.

*Post-dose timepoint is counted from start of infusion.

To understand the metabolic disposition of loncastuximab tesirine in humans, samples remaining after PK analysis is complete may be pooled among patients for potential metabolite identification.

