8.4.2 Immunogenicity

Detection of ADAs will be performed by using a screening assay for identification of antibody positive samples/patients, a confirmation assay, and titer assessment, and will be performed using the Meso-Scale Discovery Electrochemiluminescence platform (MSD-ECL). If an ADA is confirmed, a functional assay for the assessment of the neutralizing capacity of the ADA will be performed.

Approximately 6 mL of whole blood will be collected as per [Table 1](#) and [Table 5](#). Blood should be drawn from a vein away from the one used for study drug infusion.

For patients who test positive for ADAs, an additional ADA sample will be requested for testing every 12 weeks following the EOT visit until the ADA titer falls to a background level.

ADA samples must be stored at -70°C. Please refer to the laboratory manual for detailed instructions regarding specimen handling and shipment.

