2.2 Secondary Objectives

- Further evaluate the efficacy of loncastuximab tesirine
- Characterize the safety profile of loncastuximab tesirine
- Characterize the pharmacokinetic (PK) profile of loncastuximab tesirine
- Evaluate the immunogenicity of loncastuximab tesirine
- Evaluate the impact of loncastuximab tesirine treatment on health-related quality of life (HRQoL)

[REDACTED]

■ [REDACTED]

■ [REDACTED]

3 Study Design

This is a Phase 2, multi-center, open-label, single-arm study. The study will enroll approximately 140 patients.

A 2-stage design will be used, with an interim analysis for futility on the first 52 patients. If ≥ 10 patients respond (complete response [CR]+partial response [PR]), the study will proceed to complete full enrollment. Enrollment will continue during the interim analysis; however, further enrollment will be halted if futility is confirmed.

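### The three planned ADA counts use positive/negative status only, so they cannot show whether a pre-dose-positive patient's titer rose on treatment, although titer is the stated endpoint and is measured

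*Protocol*

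**What the plan says.** The immunogenicity endpoint in Protocol Section 3, Table 2 (and in the synopsis) is "Anti-drug antibody (ADA) titers and, if applicable, neutralizing activity to loncastuximab tesirine after treatment with loncastuximab tesirine". Protocol 8.4.2 describes a screening assay, "a confirmation assay, and titer assessment", with a functional assay for neutralizing capacity once an ADA is confirmed. It also asks ADA-positive patients for a further sample every 12 weeks after end of treatment until the titer returns to background. Table 5 places the first ADA sample before the Cycle 1 Day 1 infusion, with later samples at C1D15, C2D1, C3D1, every other cycle after that, and end of treatment.

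Protocol 9.9 gives the analysis: "Results from ADA testing will include tabular summarization for number/proportion of patients with positive pre-dose ADA response", followed by "number of patients with post-dose ADA response only, and number of patients with positive ADA response at any time". On the denominator it says: "The denominator will be the total number of patients tested for ADAs in the study".

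The SAP carries the objective in 2.2 ("Evaluate the immunogenicity of loncastuximab tesirine"). Its visible text has no ADA method, and Appendix 2 lists no ADA table, figure or listing. SAP 3.3 records no modification to the protocol's statistical section.

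**The concern.** The endpoint is a quantity measured after treatment, but the planned table records only whether a patient was positive and when. For patients who are negative at baseline this is enough, because any later positive result arose on treatment. For patients who are positive at baseline it is not, because status alone does not show whether exposure raised the titer, left it flat or was followed by its loss.

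Such patients can be enrolled. Exclusion 2 refers to "Known history of hypersensitivity to or positive serum human ADA to a CD19 antibody", and the Schedule of Events has no ADA sample at screening, so the criterion can act only on a result already known. Inclusion 4 admits patients with previous CD19-directed therapy. Protocol 9.9 itself plans a row for pre-dose positives.

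At stake is whether the table answers the immunogenicity objective. As listed, no row isolates what treatment did, although the titers that would show it are collected before and after dosing.

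**Working it through.** The plan states no ADA rate, titer threshold or ADA sample size, so there is no figure of its own to reproduce. The check is a logical enumeration followed by an illustration on assumed rates.

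**Step 1: sort every pattern into the three rows of Protocol 9.9.** Assume each patient has a pre-dose result and at least one post-dose result.

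| Pre-dose | Post-dose | Titer change | Row A: pre-dose positive | Row B: post-dose only | Row C: any time |
|---|---|---|---|---|---|
| negative | negative | none | no | no | no |
| negative | positive | induced | no | yes | yes |
| positive | negative | lost | yes | no | yes |
| positive | positive | flat | yes | no | yes |
| positive | positive | boosted | yes | no | yes |

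The last three lines are identical in all three rows, so a boosted patient cannot be identified from the table.

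**Step 2: what the rows do bound.** Let T = induced + boosted. Induced patients are exactly row B. Boosted patients are a subset of row A. Rows A and B do not overlap, and C = A + B. Hence B ≤ T ≤ A + B = C. The post-dose-only count is a lower bound on T, the any-time count is an upper bound, and the gap between them is the pre-dose-positive count A.

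**Step 3: illustrative size.** Inputs: N = 140 tested (planned enrolment, Protocol 4.1; assumes all are tested), pre-dose prevalence p from 1% to 10% (assumed), and fraction boosted b from 10% to 50% (assumed). The number of boosted patients outside row B is N × p × b, which is 100 × p × b percentage points of the denominator.

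| p | b = 10% | b = 25% | b = 50% |
|---|---|---|---|
| 1% (1.4 patients) | 0.14 (0.1 points) | 0.35 (0.25) | 0.7 (0.5) |
| 5% (7 patients) | 0.7 (0.5) | 1.75 (1.25) | 3.5 (2.5) |
| 10% (14 patients) | 1.4 (1.0) | 3.5 (2.5) | 7.0 (5.0) |

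The range is 0.14 to 7 patients, in practice about 0 to 7, with 1.75 patients (1.25 points) in the middle cell.

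**The case against.** The strongest reply is that the table is not wrong. Each row is a correctly labelled count, and neither document offers any row as a treatment-emergent rate. Because row A is printed, a reader can form the bounds in Step 2. All of this stands. A reader might infer that the post-dose-only row is biased low and the any-time row biased high. The documents do not support that, because bias requires a row presented as an estimate of treatment-related ADA, and none is. The accurate description is bounds that do not separate the cases.

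A reader might also infer that the plan ignores titers or leaves boosted patients uncounted. Neither follows. Titers are measured and followed after end of treatment, and a boosted patient is counted as pre-dose positive and as positive at any time. What is missing is the distinction.

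The wording in 9.9 says results will include these tabulations, so the list is not formally closed. Some text is also out of sight: there is a redaction in the opening of Protocol Section 9, and Figure 2 is not shown, although its title concerns the testing tiers. The SAP's silence is not specific to boosting, since its visible text has no ADA analysis at all. These points limit the claim to what the documents name, and they name no other ADA summary.

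Finally, exclusion 2 may leave few pre-dose positives, and the category could be derived later from stored titers. Both are fair. However, a titer multiple chosen after the data are seen is not prespecified.

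**Conclusion.** The point holds as a low-priority improvement. The three summaries in Protocol 9.9 use positive/negative status, and neither document names a summary of titer or neutralizing activity, which are the stated secondary endpoint. Among pre-dose-positive patients, boosted, unchanged and lost reactivity look the same. Post-dose-only is a lower bound and any-time an upper bound on treatment-related ADA.

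This conclusion follows from the row definitions and needs no assumed rate. Its size does: with 140 tested, 1-10% positive pre-dose and 10-50% of those boosted, about 0 to 7 patients (0.1 to 5.0 percentage points) are affected. It could be no patients at all. The endpoint is descriptive, and the ORR test is unaffected.

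**What to change.** In Protocol 9.9, and in a matching SAP section with its outputs, keep the three existing rows and add:

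- Treatment-induced ADA: pre-dose negative with any post-dose positive.
- Treatment-boosted ADA: pre-dose positive with a post-dose titer rise above a stated multiple of the pre-dose titer. The documents give no such multiple, so it should be set from assay validation and fixed before the data are analysed.
- Treatment-emergent ADA: the sum of the two.
- Peak post-dose titer, and the number of patients with neutralizing ADA.

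The samples and assays are already planned, so the cost is a few derived rows and one pre-set titer multiple. The downside is that the reported immunogenicity rate may be slightly higher than the post-dose-only count.

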4.1 Overview

This is a Phase 2, multi-center, open-label, single-arm study of the efficacy and safety of loncastuximab tesirine used as monotherapy in patients with relapsed or refractory DLBCL. The study will enroll approximately 140 patients.

A 2-stage design will be used ([Simon, 1989](#)), with an interim analysis for futility using the data on the first 52 patients (see [Section 9.3](#)). If ≥ 10 patients respond (CR+PR), the study will proceed to complete full enrollment. Enrollment will continue during the interim analysis; however, further enrollment will be halted if futility is confirmed.

The duration of the study participation for each patient is defined as the time from the date of signed written informed consent to the completion of the follow-up period, withdrawal of consent, loss to follow-up, or death, whichever occurs first.

The study will include a Screening Period (of up to 28 days), a Treatment Period (cycles of 3 weeks), and a Follow-up Period (approximately every 12 week visits for up to 3 years after treatment discontinuation).

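### One all-tested denominator for the whole ADA table would bias any post-dose-only proportion downward, probably by a small amount

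*Protocol*

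**What the plan says.** Protocol 9.9 lists three summaries: "number/proportion of patients with positive pre-dose ADA response", then "number of patients with post-dose ADA response only, and number of patients with positive ADA response at any time". The sentence that follows sets the denominator: "The denominator will be the total number of patients tested for ADAs in the study". It does not separate the rows and does not require a post-dose result.

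Table 5 (Protocol 8.4.1) sets the ADA sampling: Cycle 1 Day 1 before dosing, Cycle 1 Day 15, then before dosing on Day 1 of Cycles 2, 3, 5, 7 and every other cycle after that. An EOT sample is taken "At any time during visit day", and unscheduled samples are allowed.

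The endpoint attached to the immunogenicity objective (Protocol section 3, Table 2) is ADA titers and, if applicable, neutralizing activity.

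The SAP repeats the objective in section 2.2. It has no ADA population in section 4.1, no ADA analysis section and no ADA output in Appendix 2. Section 3.3 records no modification of the protocol's statistical section. Protocol 9.9 is therefore the only rule in force.

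**The concern.** The row headed "number of patients with post-dose ADA response only" is the one that speaks to ADA arising after exposure. Two kinds of patient count as tested but can never enter its numerator:

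- patients whose only ADA sample is the pre-dose one;
- patients who were already ADA-positive before dosing.

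Keeping them in the denominator can only pull a proportion down. The plan avoids this elsewhere: the PK population (Protocol 9.2) needs a valid pre-dose and a valid post-dose assessment, and the PRO population (SAP 4.1.4) needs a baseline and a post-baseline score. ADA has no equivalent.

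At stake is the accuracy of a descriptive immunogenicity figure. No hypothesis test or decision rule depends on it.

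**Working it through.** **Inputs from the documents.** Planned size about 140 (Protocol 4.1: "The study will enroll approximately 140 patients"). Denominator: all tested (Protocol 9.9). A patient is tested from Cycle 1 Day 1 before dosing (Table 5). The documents give no ADA rate, no number of patients without a post-dose result and no number of baseline positives, so there is no planned figure to reproduce.

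**Assumptions for illustration.** All 140 patients are tested before dosing. A post-dose-only positive is a patient with a negative pre-dose and a positive post-dose result.

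**Formula.** Let N = patients tested, m = patients with a pre-dose sample only, b = baseline positives among the rest, and X = post-dose-only positives.

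- Reported proportion = X / N
- Proportion among patients who could become post-dose-only positive = X / (N − m − b)
- Ratio of reported to at-risk proportion = (N − m − b) / N, which is below 1 whenever m + b > 0

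**Case 1: no baseline positives (b = 0), N = 140, at-risk rate 10.0%.**

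| m (assumed) | At risk | Ratio | Reported |
|---|---|---|---|
| 3 (about 2%) | 137 | 0.979 | 9.8% |
| 7 (5%) | 133 | 0.950 | 9.5% |
| 14 (10%) | 126 | 0.900 | 9.0% |

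**Case 2: both groups present, m = 7 and b = 7 (assumed), X = 10.**

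- At risk: 140 − 7 − 7 = 126
- Reported: 10 / 140 = 7.1%
- At-risk rate: 10 / 126 = 7.9%

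**What limits m and b.** To contribute to m, a patient must miss Day 15, Cycle 2 Day 1, every later scheduled sample and the EOT sample, with no unscheduled sample either. Exclusion criterion 2 (Protocol 5.2) bars patients known to be positive for ADA to a CD19 antibody, which limits b. It does not make b zero: undetected positives can still enter, and prior CD19-directed therapy is allowed under inclusion criterion 4.

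**Scale against sampling error.** The exact 95% interval for 14/140 (10.0%) is 5.6% to 16.2%. A shift of up to one percentage point is small beside it.

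**The case against.** The strongest reply is that no post-dose rate is clearly planned. Protocol 9.9 writes proportion only for the pre-dose row and number for the other two. A count is not biased by a denominator. This stands, and it makes the point conditional: the bias arises if a proportion is reported for the post-dose-only row. The denominator sentence, however, follows the whole list without restriction. If it were read as covering the pre-dose row alone, the post-dose row would have no defined denominator, which also needs a sentence.

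Three stronger readings are tempting, and the documents do not support them.

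- *Immunogenicity as a secondary endpoint is compromised.* The stated endpoint is ADA titers and neutralizing activity, and the denominator touches neither.
- *A tenth or so of patients will lack a post-dose result.* One could start from the 6.1-month historical median survival in Protocol 9.1. With exponential survival, 1 − exp(−ln 2 × (14/30.44)/6.1) = 5.1% would die within 14 days, and an allowance for missed samples could be added. That median comes from earlier salvage therapy, and a constant hazard ignores eligibility that selects against very early death (for example ECOG 0-2 and adequate organ function). No missed-sample rate is given. Missing Day 15 is also not the same as having no post-dose result, because Cycle 2 Day 1 and EOT follow.
- *All three rows have the wrong denominator.* For the any-time row, all patients tested is a defensible choice.

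It is also fair to say that an all-tested denominator is stated openly. A reader could recompute the rate if the number with post-dose results were shown, but the plan does not ask for that number.

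**Conclusion.** The point holds in a limited form. Protocol 9.9 sets one denominator for the whole ADA table, and nothing in the SAP narrows it. Any proportion reported for the post-dose-only row will be too low by the factor (pre-dose-negative patients with at least one post-dose result) / (all tested).

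The size cannot be derived from the documents and is probably small. On the assumed inputs, the understatement is 0.2 to 1.0 percentage points on a 10.0% rate, or 7.1% shown in place of 7.9% when both excluded groups are present. The direction rests on counting as post-dose-only positive just those patients with a negative pre-dose result. The primary endpoint and the ADA titer endpoint are unaffected. This is a minor correction.

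**What to change.** State the denominators by row in Protocol 9.9 and add the same rule to the SAP:

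- **Pre-dose positive:** patients with a valid pre-dose ADA result.
- **Post-dose-only positive (treatment-induced):** patients with a negative pre-dose result and at least one valid post-dose result.
- **Positive at any time:** may keep all patients tested.

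Also show the number of patients with a pre-dose sample only, so that the loss is visible.

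The cost is a few lines of text and no new samples or data. The post-dose-only proportion will be slightly higher and its denominator slightly smaller, so its interval will be a little wider.
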